### 7.1 INCLUSION CRITERIA

- I 01. Patients with T2D (drug-naïve or on antidiabetic therapy) and documented moderate renal insufficiency defined by an eGFR (based on the 4 variable Modification of Diet in Renal Disease [MDRD] equation) of  $\geq 30$  and  $< 60$  mL/min/1.73 m^2 (CKD 3A, 3B).
- I 02. Patient has given written informed consent to participate in the study in accordance with local regulations.

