#### **7.2.2 Exclusion criteria related to the diabetes or CKD history and treatment**

- E 13. Type 1 diabetes mellitus.
- E 14. HbA1c <7% or HbA1c >11% measured by the central laboratory at Screening.
- E 15. Oral antidiabetic agent or insulin use if dose not stable for 8 weeks before randomization (ie, oral agents changed during past 8 weeks or total daily basal insulin dose increased or decreased by more than 20% during the past 4 weeks).
- E 16. Use of a selective SGLT2 inhibitor (eg, canagliflozin, dapagliflozin, or empagliflozin) within 12 months prior to the trial.
- E 17. History of DKA or nonketotic hyperosmolar coma within 12 weeks prior to the Screening Visit.
- E 18. History of severe hypoglycemia that resulted in unconsciousness, coma or hospitalization within 6 months prior to the Screening Visit.
- E 19. Renal disease that required treatment with immunosuppressive therapy within the last 12 months, or renal transplant or initiation of chronic dialysis within 4 weeks prior to the Screening Visit or expected to occur during the study duration.
- E 20. History of hereditary glucose galactose malabsorption or primary renal glucosuria.
- E 21. Chronic dialysis or CKD stage 4 or 5 or requiring chronic dialysis within 6 months of Screening.

E 22. Reversible causes of renal failure such as obstruction within 6 months of Screening.

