#### 8.4 METHOD OF ASSIGNING PATIENTS TO TREATMENT GROUP

The randomized treatment kit number list is generated centrally by Sanofi. The IMPs are packaged in accordance with this list.

Patients will be randomized to receive sotagliflozin 400 mg, sotagliflozin 200 mg or matching placebo once daily during the randomized double-blind Treatment Period and Extension Period. Randomization (ratio 1:1:1) will be stratified by Screening HbA1c ( $\leq 8.5\%$  and  $>8.5\%$ ), Screening SBP ( $<130$  mmHg and  $\geq 130$  mmHg), and CKD stage at Screening (3A, 3B).

To ensure sufficient patients in each CKD stratum, enrollment will be capped for the 1st CKD stratum that reaches 390 patients (either CKD stage 3A [screening eGFR of 45 to  $<60$  mL/min/1.73 m^2] or CKD stage 3B [screening eGFR of 30 to  $<45$  mL/min/1.73 m^2]). Enrollment for the study will be completed when reaching the target number as planned.

The randomization and the treatment package allocation are performed centrally by an IRT. At the Screening Visit the Investigator or designee will contact the IRT to receive the patient number.

[REDACTED]

[REDACTED] At Visit 2 (Run-in), the IRT will be contacted for dispensing single-blinded placebo Run-in kit. At Visit 3 (Baseline), patient eligibility will be reviewed; the IRT will be contacted and corresponding treatment packages will be allocated.

After Visit 3 (Baseline), with the exception of Visit 4, the IRT is contacted again each time new treatment package(s) allocation is required by the protocol. For each randomized patient, the IRT will allocate treatment package number(s) corresponding to the treatment group assigned.

Treatment packages are allocated by the IRT using their treatment kit number.

A randomized patient is defined as a patient who is registered and assigned with a treatment kit number from the IRT, as documented in the IRT.

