2.4.5.4 Analyses of laboratory variables

Laboratory parameters will be grouped and summarized by biological function as described in [Section 2.1.4.4](#).

The summary statistics (including number, mean, median, Q1, Q3, standard deviation, minimum and maximum) of all laboratory variables (central laboratory values, changes from baseline, and/or percent change from baseline [eg, lipid parameters, albumin, total protein, hemoglobin, hematocrit]) will be calculated for each applicable visit or study assessment (screening, baseline, post-baseline time point, last on-treatment value) by treatment group. Graphical presentations may be used to examine trends over time using mean (\pm SE) and/or mean change from baseline (\pm SE) at scheduled visits (eg, creatinine, eGFR).

The incidence of PCSAs (list provided in Appendix A) at any time during the treatment-emergent adverse event period will be summarized by biological function and treatment group whatever the baseline level and/or according to the following baseline status categories:

- Normal/missing.
- Abnormal according to PCSA criterion or criteria.

For creatinine, $\geq 50\%$ change from baseline will be provided in addition to the PCSA criteria defined, ie, $\geq 150 \mu\text{mol/L}$ (Adults), $\geq 30\%$ change from baseline, $\geq 50\%$ change from baseline, and $\geq 100\%$ change from baseline will be presented. For eGFR, $\geq 50\%$ decrease from baseline will be provided in addition to the PCSA criteria defined, ie, < 15 (end stage renal disease), $\geq 15 - < 30$ (severe decrease in GFR), $\geq 30 - < 60$ (moderate decrease in GFR), $\geq 60 - < 90$ (mild decrease in GFR), and $\geq 50\%$ decrease from baseline will be presented. For parameters for which no PCSA criteria are defined, similar table(s) using the normal range will be provided.

All measurements collected during the TEAE period, including values from unscheduled visits, will be considered for the PCSA summaries. The summary tables will include patients in the safety population that have at least 1 assessment performed during the TEAE period. When a PCSA definition involves a change from baseline value, patients must also have a baseline value to be included in the summaries, and when required by the definition of the abnormality, patients must also have available laboratory normal ranges.

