A listing of patients with at least 1 post-baseline measurement PCSA or out of normal range (when no PCSA is defined) will be provided and will display the patients' entire profile over time for parameters belonging to the corresponding biological function. Individual data listings will include flags when applicable:

- Baseline values will be flagged "B".
- Normal laboratory ranges, available for most laboratory parameters, will be identified as ULN and LLN. Baseline, last on-treatment value, and individual data will be flagged "L" if the value is below the LLN and will be flagged "H" if it is above the ULN.
- Laboratory PCSA criteria will be used for the corresponding laboratory parameters. Values reaching a PCSA limit will be flagged (+, ++, -, or -- depending upon the direction and level of the abnormality). Flags for WBC and differential counts will be determined using data expressed in international units.

For parameters whose PCSA criteria are based on multiples of ULN, the parameter's value will also be expressed as multiples of ULN in the individual data presented.

Drug-induced liver injury

The liver function tests, namely AST, ALT, alkaline phosphatase, and total bilirubin, are used to assess possible drug-induced liver toxicity. The proportion of patients with PCSA values at any post-baseline visit by baseline status will be displayed by treatment group for each parameter. The proportion of patients with PCSA values at any post-baseline visit will also be displayed by duration of exposure for each treatment group (only if a tabulation summary is necessary).

Listing of possible Hy's law cases identified by treatment group (eg, patients with any elevated $\text{ALT} > 3 \times \text{ULN}$, and associated with an increase in bilirubin $\geq 2 \times \text{ULN}$) with ALT, AST, alkaline phosphatase, total bilirubin, and the following complementary parameters if available: conjugated bilirubin and prothrombin time/international normalized ratio, creatine phosphokinase, serum creatinine, complete blood count, anti-HAV IgM, anti-HBc IgM, anti-HCV and HCV RNA,

anti-CMV IgM and anti-HEV IgM antibodies, auto-antibodies: anti-nuclear, anti-DNA, anti-smooth muscle, Epstein-Barr virus, herpes viruses, and anti-LKM.

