CLcr (mL/min) (Estimated creatinine clearance based on the Cockcroft-Gault equation)	<15 (end stage renal disease) ≥15 - <30 (severe decrease in GFR) ≥30 - <60 (moderate decrease in GFR) ≥60 - <90 (mild decrease in GFR) ≥90 (normal GFR)	FDA draft Guidance 2010 Pharmacokinetics in patients with impaired renal function-study design, data analysis, and impact on dosing and labeling
eGFR (mL/min/1.73 m ²) (Estimate of GFR based on an MDRD equation)	<15 (end stage renal disease) ≥15 - <30 (severe decrease in GFR) ≥30 - <60 (moderate decrease in GFR) ≥60 - <90 (mild decrease in GFR) ≥90 (normal GFR)	FDA draft Guidance 2010 Pharmacokinetics in patients with impaired renal function-study design, data analysis, and impact on dosing and labeling
Creatinine	≥150 µmol/L (Adults) ≥30% change from baseline ≥100% change from baseline	Benichou C, 1994
Uric Acid Hyperuricemia Hypouricemia	>408 µmol/L <120 µmol/L	Harrison- Principles of internal Medicine 17 th ed, 2008
Blood Urea Nitrogen	≥17 mmol/L	
Chloride	<80 mmol/L >115 mmol/L	
Sodium	≤129 mmol/L ≥160 mmol/L	
Potassium	<3 mmol/L ≥5.5 mmol/L	FDA February 2005
Total Cholesterol	≥7.74 mmol/L	Threshold for therapeutic intervention
Triglycerides	≥4.6 mmol/L	Threshold for therapeutic intervention
Lipasemia	≥3 ULN	
Amylasemia	≥3 ULN	

CRITERIA for POTENTIALLY CLINICALLY SIGNIFICANT ABNORMALITIES
for Phase 2/3 studies (oncology excepted)
(From BTD-009536 May 21, 2014)

Parameter	PCSA	Comments
Glucose		
Hypoglycaemia	≤3.9 mmol/L and <LLN	ADA May 2005
Hyperglycaemia	≥11.1 mmol/L (unfasted); ≥7 mmol/L (fasted)	ADA January 2008
HbA1c	>8%	
Albumin	≤25 g/L	
CRP	>2 ULN or >10 mg/L (if ULN not provided)	FDA September 2005
Hematology		
WBC	<3.0 Giga/L (Non-Black); <2.0 Giga/L (Black) ≥16.0 Giga/L	Increase in WBC: not relevant To be interpreted only if no differential count available
Lymphocytes	>4.0 Giga/L	
Neutrophils	<1.5 Giga/L (Non-Black); <1.0 Giga/L (Black)	International Consensus meeting on drug-induced blood cytopenias, 1991 FDA criteria
Monocytes	>0.7 Giga/L	
Basophils	>0.1 Giga/L	
Eosinophils	>0.5 Giga/L or >ULN (if ULN ≥0.5 Giga/L)	Harrison- Principles of internal Medicine 17 th ed, 2008
Hemoglobin	≤115 g/L (Male); ≤95 g/L (Female) ≥185 g/L (Male); ≥165 g/L (Female) Decrease from Baseline ≥20 g/L	Criteria based upon decrease from baseline are more relevant than based on absolute value. Other categories for decrease from baseline can be used (≥30 g/L, ≥40 g/L, ≥50 g/L)

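### The eGFR abnormality table uses absolute bands that overlap the trial's entry range, so two of its rows mislead and its patient listing selects nearly everyone

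*SAP*

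**What the plan says.** Protocol 7.1 (I 01) admits patients with "documented moderate renal insufficiency defined by an eGFR (based on the 4 variable Modification of Diet in Renal Disease [MDRD] equation) of" at least 30 and below 60 mL/min/1.73 m². Protocol 7.2.2 (E 21) excludes "Chronic dialysis or CKD stage 4 or 5 or requiring chronic dialysis within 6 months of Screening". Protocol 8.4 aims for a roughly even mix of stages 3A and 3B: "enrollment will be capped for the 1st CKD stratum that reaches 390 patients", out of about 780.

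SAP Appendix A takes its criteria for potentially clinically significant abnormalities (PCSAs) from a sponsor list for Phase 2/3 studies in general. For eGFR these are absolute levels with no baseline condition. The band from 30 to <60 is labelled "moderate decrease in GFR", and 60 to <90 is labelled a mild decrease. SAP 2.4.5.4 orders these rows for eGFR. It says that a ≥50% "decrease from baseline will be provided in addition to the PCSA criteria defined, ie" the four bands below 90. A patient counts if the criterion is met at any time in the treatment-emergent period.

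Results may be shown regardless of baseline, by baseline status, or both. Baseline status has two categories: normal or missing, and "Abnormal according to PCSA criterion or criteria". The same section orders "A listing of patients with at least 1 post-baseline measurement PCSA".

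SAP 2.4.5 defines a PCSA as an abnormal value of medical importance. It also says that laboratory parameters which the protocol names as efficacy endpoints get no PCSA summary. Change in eGFR is such an endpoint (Protocol 9.1.3, SAP 2.1.3.3).

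**The concern.** The band called a moderate decrease is the entry range itself. A patient whose kidney function never changes is counted in it. A patient who goes from 55 to 62 has improved, yet is tabulated under mild decrease. Because both rows are absolute levels, a drug that lowers eGFR moves patients out of them, so an arm with real harm shows fewer such abnormalities than placebo.

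Protocol 4.5 names small falls in glomerular filtration rate as a class effect, so this table will be read with care. Two of its rows cannot be read at face value, and a listing meant to pick out notable patients picks out nearly all of them.

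**Working it through.** **Stated figure.** The plan gives no expected incidence for these rows, so there is nothing to reproduce. The central point follows from the text alone; the simulation only sizes it.

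**Text check.** Take an unchanged patient with entry value x, where 30 ≤ x < 60. The moderate-decrease criterion is 30 ≤ value < 60, so it is met with zero change. Now take any patient with baseline below 60 and a later value of at least 60. That value is above baseline, yet it is counted as a mild decrease.

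**Inputs from the documents.** Screening eGFR is 30 to <60 (Protocol 7.1). Baseline is the mean of the pre-dose values (SAP 2.1.1). There are eight on-treatment chemistry visits, at Weeks 2, 4, 8, 12, 18, 26, 39 and 52 (Protocol 1.2). A patient counts after one qualifying value (SAP 2.4.5).

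**Assumptions, not in the documents.** True eGFR is spread evenly around the entry range. Within-patient SD is 5 (range 3 to 7). The background slope is −2 per year. The drug-related drop d is constant at 0, 3 or 5. All are in mL/min/1.73 m².

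**Model.** Value at week w = true level − d − 2·(w/52) + error. Patients are kept if the screening value is in 30 to <60. Each row is the share of patients with at least one qualifying value, unless two consecutive visits are stated. Each scenario used several hundred thousand simulated patients.

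**Results at SD 5:**

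| Row | d = 0 | d = 3 | d = 5 |
|---|---|---|---|
| 30 to <60 (moderate decrease) | about 98% | 96–97% | 94–95% |
| 60 to <90 (mild decrease) | 22.5% | 14.6% | 10.2% |
| 15 to <30 | 27% | 37% | 43% |
| Creatinine up ≥30% | 23–24% | 44% | 59% |
| Baseline 45 to <60, below 45 at two consecutive visits | 26.5% | 44.0% | 56.7% |
| Baseline 30 to <45, below 30 at two consecutive visits | 20.8% | 36.6% | 49.0% |

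The first two rows fall as harm rises; the other four rise. For d = 0, 3 and 5 the mild-decrease row is about 13%, 6% and 3% at SD 3, and about 32%, 24% and 18–19% at SD 7. With no drug effect, about 80% of its flags come from patients with baseline below 60, across SD 3 to 7. Every simulated patient has at least one value below 90, so the listing takes everyone.

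**Second model.** Proportional error with a CV of 5%, 8% or 12% and no slope gives the same picture. With no effect the moderate row is 99.1%, 98.5% and 97.7%, and the mild row is 14.4%, 22.8% and 33.3%. A true 10% fall in eGFR cuts the mild row to 2.1%, 8.5% and 18.7%.

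**What the creatinine rows catch.** In the SAP's MDRD formula eGFR varies as creatinine to the power −1.154. A 30% rise gives 1.30^−1.154 = 0.739, a 26% fall; a 50% rise gives 1.50^−1.154 = 0.626, a 37% fall. So 60 becomes 60 × 0.739 = 44.3. A patient starting at 50 drops below 45 after a 10% fall, which is a creatinine rise of only (50/45)^(1/1.154) − 1 ≈ 10%. The ≥30% row does not see that change.

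**The case against.** The strongest reply is that renal decline is well covered, and most of it stands. Entry requires at least 30, so the 15 to <30 and <15 rows are almost entirely new worsening, and the simulation shows the former moving the right way. The ≥50% row and the creatinine ≥30%, ≥50% and ≥100% rows refer to the patient's own baseline. SAP 2.4.4.3 gives eGFR by visit and stratum, and >50% decline and ESRD with Kaplan–Meier plots. SAP 2.1.4.2 defines renal events of special interest, and SAP 2.4.5.2 adds an acute renal failure search. A reader might infer that worsening kidney function goes uncounted in this trial. The documents do not support that.

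A reader might also infer that the split by baseline status is empty throughout. The wording can be read criterion by criterion, and then the split works for the rows below 30. It still does not rescue the two rows at issue. Nearly everyone is already abnormal for the moderate row. For the mild row, a rise from the entry range would appear as a new abnormality. Neither reading separates 3A from 3B.

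The labels can be defended as a renal-function classification, since Appendix A also lists ≥90 as normal. The listing shows each patient's full profile with baseline flagged, so direction can be recovered. But SAP 2.4.5.4 drops the normal row and presents the rest as abnormality criteria. Nor is every mild-decrease flag an improvement: baseline is a mean, and under the assumptions about 3% to 7% of patients have one of 60 or more. With a drop of 5 at SD 5, about 35% of mild flags are not rises from below 60.

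Protocol 11.4.3.5 permits laboratory shift tables, but SAP 2.4.5.4 plans none for eGFR.

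**Conclusion.** The point holds as a defect of presentation. In this population the 30 to <60 row is near 100% in every arm without any decrease. The 60 to <90 row mostly counts values above baseline when there is no drug effect, and it falls as harm rises. The listing selects essentially every patient. SAP 2.4.5 and SAP 2.4.5.4 also disagree on whether eGFR should have an abnormality summary at all.

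Two things lack a count: 3A patients worsening to below 45, and the 15 to <30 row by baseline stage. Safety data are descriptive with no systematic testing (SAP 2.4.5), so no inference depends on this table. It should be corrected, but it does not threaten the trial's conclusions.

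The overlap of bands and entry range is certain from the text. Every percentage rests on the assumed within-patient variability, slope and drug effect. The direction was the same at every SD and CV tried.

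**What to change.** In SAP 2.4.5.4 and Appendix A, for this study:

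- Remove 30 to <60 and 60 to <90 as eGFR abnormality rows. Keep <15, 15 to <30 and ≥50% decrease.
- Add worsening from the patient's own baseline CKD stage with at-risk denominators. For baseline 45 to <60, use <45, <30 and <15. For baseline 30 to <45, use <30 and <15.
- Make two consecutive visits the main display. At SD 5 with no drug effect, a single-visit rule flags about 57% of the first group falling below 45 and about 49% of the second falling below 30, so it is too noisy to lead with.
- State how averaged baselines of 60 or more, or below 30, are handled.
- Split the eGFR table by baseline 3A versus 3B, and base the eGFR listing on these criteria.
- Reconcile the SAP 2.4.5 rule on efficacy parameters with SAP 2.4.5.4.

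The cost is SAP wording, one reprogrammed table and one listing, all from data already collected. The eGFR table would no longer pool row for row with other studies that use the generic list; keeping the generic rows in an appendix avoids that. SAP 1.6 says top-line results from the first step were already reported, so the version history should record the change as made after that.

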2.4.5.5 Analyses of vital sign variables

The summary statistics (including number, mean, median, Q1, Q3, standard deviation, minimum and maximum) of heart rate, temperature and respiratory rate (observed values or mean observed values, and changes from baseline) will be calculated for each visit or study assessment (baseline, each post-baseline time point, last on-treatment value) by treatment group.

The incidence of PCSAs at any time during the TEAE period will be summarized by treatment group for SBP, DBP, and HR. All measurements collected during the TEAE period, including unscheduled ones, will be considered for the PCSA summaries. The summaries will include patients in the safety population who have at least 1 assessment performed during the TEAE period. When a PCSA definition is based on change from baseline, patients must have a baseline to be included in the summaries.

A listing of patients with at least 1 post-baseline PCSA will be provided and will display the patient's profile over time of all vital sign parameters. Individual data listings will include the following flags:

- Baseline values will be flagged "B".
- Parameter values reaching a PCSA limit will be flagged ("+" or "-" depending on the direction).

2.4.5.6 Analyses of electrocardiogram variables

Shift tables will be provided to present ECG status according to baseline status (Normal/Missing, Abnormal) for each treatment group during the TEAE period. Supportive listings of patients with abnormal ECG status at any post-baseline visit will be provided.

2.4.5.7 Analyses of physical examination variables

Shift tables will be provided to present physical examination findings by body system according to baseline status (Normal/Missing, Abnormal) for each treatment group during the TEAE period. Supportive listings of patients with abnormal findings at any post-baseline visit will be provided.

2.4.5.8 Bone Mineral Density

The summary statistics (including number, mean, median, Q1, Q3, standard deviation, standard error, minimum and maximum) of BMD (lumbar spine, total hip, femoral neck) (observed values, and changes from baseline, percent changes from baseline) will be provided at Week 52 by treatment group. The analysis will include BMD measurements obtained during the study, regardless of IMP discontinuation and/or introduction of rescue therapy based on the safety population. The number (%) of patients will be summarized by visit for each T-score category: normal (T-score ≥ -1.0); low bone density (T-score > -2.5 and < -1); osteoporosis (T-score ≤ -2.5).

2.4.6 Analyses of pharmacokinetic variables

Plasma concentrations of sotagliflozin and its 3-O-glucuronide metabolite will be summarized in the PK population (see Section 2.3.3) by visit and nominal sampling times (pre-dose at Weeks 4, 18, 26, and 52, 3 hours post-dose at Weeks 26, and 52) in the sotagliflozin groups, using descriptive statistics (Number, geometric mean, coefficient of variation, median, minimum and maximum). Individual plasma concentrations of sotagliflozin and its 3-O-glucuronide metabolite at nominal sampling times will be listed.

2.5 DATA HANDLING CONVENTIONS**2.5.1 General conventions**

The following formulas will be used for computation of parameters.

HbA1c

The formula to convert HbA1c from Diabetes Control and Complications Trial (DCCT) aligned value to International Federation of Clinical Chemistry and Laboratory Medicine (IFCC) standardized value is:

$$\text{IFCC-HbA1c (mmol/mol)} = (\text{DCCT} - \text{HbA1c (\%)} - 2.15) \times 10.929.$$

Renal function formulas

The estimated GFR (mL/min/1.73m²) will be calculated using the 4 variable Modification of Diet in Renal Disease (MDRD) formula:

$$\text{Standard unit: eGFR (mL/min/1.73m}^2\text{)} = 175 \times [\text{Serum Creatinine } (\mu\text{mol/L})/88.4]^{-1.154} \times \text{Age (year)}^{-0.203} \times 1.212 \text{ (if Black)} \times 0.742 \text{ (if Female)}.$$

$$\text{Conventional unit: eGFR(mL/min/1.73m}^2\text{)} = 175 \times [\text{Serum Creatinine (mg/dL)}]^{-1.154} \times \text{Age (year)}^{-0.203} \times 1.212 \text{ (if Black)} \times 0.742 \text{ (if Female)}.$$

Urine ACR

Standard unit: $UACR (mg/g) = \text{Urine Albumin (mg/dL)} / (\text{Urine Creatinine (mmol/L)} \times 11.31) \times 1000$.

Conventional unit: $UACR (mg/g) = \text{Urine Albumin (mg/dL)} / \text{Urine Creatinine (mg/dL)} \times 1000$.

Urine GCR

Standard unit: $\text{Urine GCR} = \text{Urine Glucose (mmol/L)} / \text{Urine Creatinine (mmol/L)}$.

Conventional unit: $\text{Urine GCR} = \text{Urine Glucose (mg/dL)} / \text{Urine Creatinine (mg/dL)}$.

Calculation of LDL-C

When TG is lower than or equal to 4.52 mmol/L(400 mg/dL), LDL-C is calculated using the Friedewald equation as:

- In Standard unit(mmol/L), $TC - HDL-C - TG/2.17$.
- In Conventional unit (mg/dL), $TC - HDL-C - TG/5$.

